4.1 Sample Size

There is an estimated 12,500-15,000 people living with SCD in the UK^{xvii}. Our patient sample size is based upon an estimated minimum proportion of the total population of patients with SCD we aim to enrol onto the digital platform and wearables pilot study, assuming not all patients will be reached by the initial programme launch through the Sickle Cell Society and partnering trusts, and that of those who are, not all will provide consent or be interested in participating. As such, our starting goal is to recruit 2% of the total UK SCD patient population, at 300 patients.

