4.2 Data Sources, Access and Flow

From the starting point of sources including hospital Electronic Medical Records (EMRs), open data, and Hospital Episode Statistics (HES), the data platform will integrate written medical and primary care records from GPs, structured and unstructured EMIS/TPP records, as well as genetic information through external organisations such as 23andMe, following full patient consent. With additional wearables collected data (Section 4.3), these sources will be combined within a specialised SCD unified data platform to allow the application of a set of advanced algorithms, providing granular analysis of key patient metrics.

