4.3 Wearable & App Data Points

Following specification of the most crucial metrics, live data points will be integrated into the unified data platform directly from patients through the use of wearables and ongoing monitoring of factors, or through optional manual input of additional information, such as a pain scale of mood, through the platform's mobile app by patients. These include:

Metric	Rationale
Heart Rate	A fast heart rate is linked to anaemia and low blood O ₂ , stress, and panic attacks.
Blood O₂ Saturation	Low arterial blood oxygen saturation is common in SCD, and Obstructive Sleep Apnoea is also highly prevalent in patients with SCD.
Body Temperature	Raised or decreased temperatures are linked to crises, with low body temperatures known to trigger vasoconstriction. High temperatures can also be an indication of infection and in turn trigger crises.
Blood Pressure	Blood pressure is known to be lower in SC anaemia, with relative hypertension linked to an increased risk of stroke, pulmonary hypertension, renal dysfunction & death. This can also be used as an important indicator of stress.
ECG Abnormalities	ECG abnormalities are common in SCD & early identification / intervention can help to prevent serious cardiac events, e.g. Myocardial Infarction during VOC.
Sleep Cycles	Disrupted sleep cycles / patterns are linked to increased pain and periods of crisis.
Fitness & Activity	Low activity levels may be an indicator of the onset of a crisis, and certain exercises are linked to relieving pain.
Nutrition / Diet / Medications taken	Can be an important indicator of emotional wellbeing & pain levels, with disrupted eating patterns or loss of appetite potentially indicating periods of chronic pain or VOC.
Pain and Symptoms	Provides a direct monitor of patient wellbeing and will support correlation of metrics with symptoms of SCD pathologies.

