7.2 Patient Withdrawal

Patients may voluntarily withdraw from the study at any time, as protected by GDPR, or be dropped from it at the discretion of the responsible clinician (investigator) at the NHS Trust. Patients may be withdrawn from the study if any of the following occur:

Patient or parent withdrew consent

Lost to follow-up

Death

Administrative problems

For patients who are lost to follow-up, the investigator will show 'due diligence' by documenting steps taken to contact the patient, such as dates of telephone calls, and mailings.

8. Statistical Analyses

An initial high-level investigation using descriptive analysis will be conducted across all variables in order to identify key trends and insights, from which further correlations and statistical significance will be tested. This will predominantly be performed using IBM SPSS Statistics 24 and Microsoft Excel, collected data analysed for outliers through Boxplot and Q-Q Plots, for normal distribution using Shapiro-Wilks testing, and for homogeneity of variance using Levene's testing. Due to the exploratory nature of the study, hierarchical stepwise regression of the outlined data points (Section 4.2 & 4.3) will be conducted, and any outliers detected through assumption testing will not be immediately excluded from analyses, instead further investigated to identify any clinically significant causes. For data that do not violate these assumptions, either independent t-tests (for experiments with two experimental groups) or one-way ANOVA (for experimental groups of 3 or more) will be performed, with Bonferroni post-hoc testing. Those that do violate these assumptions will undergo non-parametric Kruskal-Wallis testing. Each analysis will be based upon demographic variables, such as age and gender, correlated against genetic and clinical variables including hospital admissions, comorbidities, genotype, phenotype, and wearables collected data (Section 4.3). Those with p-values below 0.05 will be considered as statistically significant and undergo further study.

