An additional focus for the study regards data collected over extended periods of time and the progression of the disease state over this period, therefore requiring the inclusion of two independent variables. For such data, this will require Mauchly's test for sphericity in addition to Shapiro-Wilks testing for normal distribution. These data will then be tested for statistical significance using a two-way repeated measures ANOVA with a Bonferroni adjustment. Each step of the analytical output will be reported alongside changes in variance and F change, and collinearity of the independent variables will be investigated within the regression model.

This statistical analysis will in part feed into and be supported by the data platform's advanced AI and ML algorithms. However, the primary purpose of the AI technology will revolve around the predictive element of this study, highlighting potential outcomes and suggestions for optimal treatment pathways based upon the statistical analysis conducted, and key trends or associations identified.

9. Administrative Procedures

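### Section 8 selects predictors by stepwise regression at p<0.05 and bases the AI's predictions and treatment-pathway suggestions on that analysis, with p-values and R-squared that ignore the selection

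*Protocol*

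**What the plan says.** All of the analysis text is in Protocol Section 8 (Statistical Analyses).

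- **Selection method.** The protocol justifies the regression by the study's exploratory character and states that "hierarchical stepwise regression of the outlined data points (Section 4.2 & 4.3) will be conducted".
- **Candidate pool.** Section 4.3 tabulates nine metrics, and "live data points will be integrated into the unified data platform directly from patients through the use of wearables". Section 4.2 adds hospital records, HES, open data and primary care records, including "structured and unstructured EMIS/TPP records, as well as genetic information through external organisations such as 23andMe". Neither section gives a number of variables.
- **Decision rule.** "Those with p-values below 0.05 will be considered as statistically significant and undergo further study".
- **Reporting.** "Each step of the analytical output will be reported alongside changes in variance and F change". A collinearity check is also planned.
- **Use of the results.** Section 8 names prediction as the main purpose of the AI technology: "highlighting potential outcomes and suggestions for optimal treatment pathways based upon the statistical analysis conducted".
- **Size.** Section 4.1: "our starting goal is to recruit 2% of the total UK SCD patient population, at 300 patients".

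**The concern.** A stepwise procedure looks at every candidate, keeps the one with the largest F, and repeats. The F-change p-value printed at each step is calculated as if that variable had been the only one considered. It therefore understates how easily chance alone produces such a value. The R-squared of the final model is too high for the same reason, because the terms were picked for fitting these particular patients.

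In a purely descriptive report this would be a matter of interpretation. Here the analysis has a further use. Section 8 makes it the basis of predicted outcomes and treatment-pathway suggestions, and Section 2.1 says that patients will see the insights and use them in managing their care. A chance association could therefore pass from a selection step into a suggestion with its nominal significance as its only support.

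**Working it through.** **Inputs from the protocol**
- n = 300 (Section 4.1). The figure reproduces from the upper end of the stated population range: 0.02 × 15,000 = 300. The lower end gives 0.02 × 12,500 = 250. I take 300 as given.
- Significance level 0.05 per test (Section 8).
- Nine listed metrics (Section 4.3). The variables arising from Section 4.2 are not counted.

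**Assumptions**
- Number of candidates k: 9 (the listed metrics, one variable each) up to 100. Each wearable stream can yield several variables, and Section 4.2 adds records and genetic data.
- One continuous outcome, independent normal predictors, and no true association.
- A free stepwise search with entry at p<0.05 and removal at p>0.10.

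**Step 1: approximate formula.** With k independent candidates and no signal, the chance that at least one meets the entry criterion is 1 − 0.95^k.
- k = 9: 1 − 0.95^9 = 0.37
- k = 30: 1 − 0.95^30 = 0.79
- k = 100: 1 − 0.95^100 = 0.99

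**Step 2: simulation.** Null datasets of 300 patients (600 per row, 300 for k = 100), with each final model scored on 2,000 fresh subjects.

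| k | Formula | Any term selected | Mean false terms | Apparent R² | R² in new subjects |
|---|---|---|---|---|---|
| 9 | 37% | 36% | 0.4 | 0.008 | −0.012 |
| 20 | 64% | 62% | 1.0 | 0.018 | −0.022 |
| 30 | 79% | 77% | 1.6 | 0.029 | −0.034 |
| 50 | 92% | 94% | 2.7 | 0.049 | −0.055 |
| 100 | 99% | 99% | 5.5 | 0.098 | −0.111 |

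Whenever a term was selected, the overall F test of the final model also had p<0.05. Other runs of the same design gave 38% at k = 9, 79-80% at k = 30 and 99-100% at k = 100, which is simulation error.

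**Step 3: what moves these figures**
- *Correlation lowers them.* With predictors correlated at 0.3, a null model was selected in about 67% of studies at k = 30 and 96% at k = 100.
- *Pre-ordered blocks* would also lower them, by an amount that cannot be computed because no blocks are given.
- *Several outcomes raise them.* Section 3.1 names acute illness, chronic illness and healthcare utilisation. With nine candidates and three independent outcomes there are 9 × 3 = 27 tests, and 1 − 0.95^27 = 0.75.

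**The case against.** **The study is exploratory, and significant findings go on to further study.** This is the strongest reply, and it stands in part: Section 8 does not claim confirmation. It also says that the statistical analysis feeds the algorithms only in part. But the further study is not defined as a check in new patients, and the suggestions are said to rest on this analysis and not on its follow-up.

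**Validation may be set out elsewhere.** This stands. A reader might infer that no patients will be held out and that the AI will be judged on the patients used to build it. The protocol does not say so. It is silent, and model validation is something a statistical analysis plan can supply. The point made here is narrower: the protocol itself fixes the selection method, the statistics reported and the link to the suggestions.

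**Hierarchical may mean analyst-ordered blocks.** Variance change and F change per block are ordinary output for that design, and terms entered in a pre-set order do not suffer from this problem. However, the protocol also says stepwise and gives no blocks or order, so the extent of the search is open. The criticism applies only to terms chosen by search.

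**The candidate numbers are assumed.** They are. A reader might infer that noise is bound to look predictive. That is close to true only towards 50 to 100 candidates. With nine candidates and one outcome, most null studies would select nothing. Apparent R-squared is also small throughout, so the harm is mainly false significance and not impressive fit.

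**Could the position be worse because fewer patients supply usable data?** Section 2.1 reports 57.9% compliance in week 4, and it is tempting to apply this to the 300. That figure comes from an earlier study that required daily manual entry. Section 2.1 uses it to argue for automated collection, so it is not an evaluable fraction for this study.

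**Is 300 too few for the predictors?** Section 4.1 presents 300 as a recruitment goal for a pilot. With no stated number of candidates, inadequacy on this ground cannot be shown.

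**Conclusion.** The point holds in this limited form. If Section 8 is followed as written, terms picked by the stepwise search will carry p-values and R-squared that ignore the selection, and the AI's predictions and treatment-pathway suggestions will be based on them.

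The size depends on a candidate count that the protocol does not give. For 300 patients, one outcome and independent noise predictors under a free search, the chance of a nominally significant model is about 36-38% with 9 candidates, about 80% with 30 and about 99% with 100. Mean apparent R-squared is about 0.01 to 0.10, against about -0.01 to -0.11 in new patients. The method should be changed. It does not follow that every model from this study would be false, nor that validation is certain to be absent.

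**What to change.** Revise Section 8 as follows.

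1. Replace stepwise selection with a penalised regression (for example elastic net) or a pre-specified model, with age, sex and genotype forced in.
2. Repeat every selection and tuning step, including any AI or machine-learning step, inside repeated cross-validation or bootstrap that samples whole patients.
3. Report optimism-corrected discrimination and calibration in place of apparent fit.
4. Do not report F-change p-values for terms selected from the data.
5. State that treatment-pathway associations are hypothesis-generating until checked in new patients.

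Resampling suits this study better than a single hold-out. Section 6 names two trusts of unequal size (potential cohorts of 1,324 and 418) plus Sickle Cell Society recruits, so leaving out one trust would be close to a single unbalanced split. Setting aside the last 20-25% enrolled would leave 0.20 × 300 = 60 to 0.25 × 300 = 75 patients, all from the three-month enrolment shown in Section 5.

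The cost is protocol wording, some programming, and performance figures that will look less favourable. No further patients or visits are needed to make these changes.

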Similarly, patients living with SCD are faced with an increasing risk of chronic complications and organ damage (e.g. renal failure, pulmonary hypertension) as they age, and the need to understand the currently uncertain cause underlying the progression to these states in certain patients will be essential in detecting, predicting and preventing these complications in the future. Long term studies following large cohorts of patients through ongoing and in-depth data collection are currently severely lacking, clinicians as a result unable to definitively identify those patients at risk of advancing to these severe disease states or establish which interventions would provide the best outcomes for these patients, based on their demographics, genetics, comorbidities and disease progression thus far. Although a number of studies have investigated the associated metrics linked to renal failure within their SCD patient cohorts, previous work having identified male gender, proteinuria, cardiovascular diseases, and transfusions as potential risk factors in acute renal failure, these findings are based solely upon databases comprised of inpatient services, inpatient admissions, outpatient services, and prescription drug claims^{xi}. While certainly an important part of establishing the potential causes or triggers of renal failure, such data again looks only at the patient profile at their most severe points in their pathway, and subsequently miss the complex network of additional factors which may cause the gradual progression to renal failure over the years.

These frequently flagged issues in providing the best standards of care to their patients demonstrate the importance of a better understanding of the specific metrics involved, correlating the factors that have historically shown a strong likelihood of progression to a severe disease state, and matching patients with others of a similar profile in terms of areas such as age, gender, comorbidities and genotype who may be at a more advanced stage of their disease, in order to

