see which treatment options have offered the best outcomes. Closer monitoring of patients beyond this on a day-to-day basis provides the ability to change treatment pathways or provide interventions in a preventative manner, identifying potential adverse events or outcomes before the point of no return. The aim of this study is therefore to build a digital patient profile which will help to support the study of SCD's natural history, produce risk stratifications, predict long-term impacts, and create a correlation matrix of metrics signalling, for example, a potential crisis or the early stages of progression to renal failure, flagging issues earlier in the cycle for faster interventions, or even raising the alarm before a crisis is triggered. Patients will have full visibility of their data and the resulting insights to manage their own care more effectively and pre-emptively, with support from clinicians through earlier detection of adverse events.

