The main objective of this project is to establish a digital patient profile to identify and monitor for the key risk factors or triggers around SCD pathologies, such as VOC and organ damage, as well as the best treatment options for these patients. Furthermore, the resulting unified platform will help to collate the necessary information needed to empower patients in managing their own care, and access specialist clinician advice as and when they need it.

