3.1 Primary Aim

The primary aim is to study the continuous pattern of vital parameters, collected over a long duration, within a sample cohort of consenting patients with SCD in order to determine how these relate to acute and chronic illnesses, as well as healthcare utilisation.

This will be through the creation of a unified data platform – comprising historical patient data, a full genetic background, and real-time patient data – through the incorporation of a wearable device into patient disease management.

Through this, the intended outcome will be improved quality and duration of life in patients.

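### Group tests in Section 8 cannot hold age constant, so between-patient links of wearable metrics with chronic complications may be created or hidden by age

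*Protocol*

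**What the plan says.** Section 8 of the protocol assigns group comparisons by assumption checks. Where normality and equal variance hold, "either independent t-tests (for experiments with two experimental groups) or one-way ANOVA (for experimental groups of 3 or more) will be performed". Otherwise, "Those that do violate these assumptions will undergo non-parametric Kruskal-Wallis testing". On what is compared, it says only: "Each analysis will be based upon demographic variables, such as age and gender, correlated against genetic and clinical variables"; the clinical side includes admissions, comorbidities and the wearable data.

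Section 8 also plans a hierarchical stepwise regression of the data points in Sections 4.2 and 4.3, with F change and collinearity reported. Those two sections list data sources and metrics, and neither names age. Longitudinal data go to a two-way repeated measures ANOVA. Results with p below 0.05 go on to further study, and the platform's predictions and treatment suggestions draw on the associations found.

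The goals are broader than describing age groups. Section 3.1 sets out to study vital parameters and to "determine how these relate to acute and chronic illnesses, as well as healthcare utilisation". Section 3 wants to "identify and monitor for the key risk factors or triggers around SCD pathologies, such as VOC and organ damage". Section 2.1 intends to "create a correlation matrix of metrics signalling, for example, a potential crisis or the early stages of progression to renal failure".

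On age, Section 6.1 admits patients from 5 years with no upper limit. Section 2.1 states an "increasing risk of chronic complications and organ damage (e.g. renal failure, pulmonary hypertension) as they age", and speaks of "matching patients with others of a similar profile in terms of areas such as age, gender, comorbidities and genotype" when looking at treatment options.

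**The concern.** The study has no randomised arms, so patients with and without a complication are self-formed groups. By the protocol's own account of chronic complications, the affected group will tend to be older. Any metric that drifts with age will then differ between the groups even if it has no connection with the complication among patients of the same age. If age pushes the metric the opposite way to a real link, the real link shrinks, disappears or changes sign.

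The t-test, one-way ANOVA and Kruskal-Wallis have no term for age. A stepwise regression could carry one, but unless age is forced in, selection may leave it out. What is at stake is the quality of the leads that pass the 0.05 screen and feed the platform's predictions.

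**Working it through.** **Inputs from the protocol.** Target sample size 300 (Section 4.1); significance level 0.05 (Section 8, taken as two-sided because the side is not stated); ages from 5 with no upper limit (Section 6.1); risk of chronic complications rising with age, direction only (Section 2.1).

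**The plan's own figure.** Section 4.1 takes 2% of an estimated 12,500 to 15,000 patients: 0.02 × 15,000 = 300 and 0.02 × 12,500 = 250. The 300 reproduces from the upper end. It is a recruitment goal, not a power calculation.

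**Assumptions.** The protocol gives no size for any age relation. Let r1 be the correlation of age with the metric and r2 that of age with the complication, each varied from 0 or 0.1 to 0.4.

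**1. Creating an association.** With no link among patients of the same age, the expected raw correlation is r1 × r2. By Fisher's z, the standard error is 1/√(N − 3) = 1/√297 = 0.0580 at N = 300. For r1 = r2 = 0.3, the raw correlation is 0.09, atanh(0.09) = 0.0902, and 0.0902/0.0580 = 1.555. The chance of exceeding ±1.96 is then 34%. The other cases:

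| r1, r2 | raw correlation | p < 0.05, N = 300 | p < 0.05, N = 150 |
|---|---|---|---|
| r1 = 0 | 0 | 5% | 5% |
| 0.1, 0.1 | 0.01 | 5% | 5% |
| 0.2, 0.2 | 0.04 | 11% | 8% |
| 0.2, 0.3 | 0.06 | 18% | 11% |
| 0.3, 0.3 | 0.09 | 34% | 19% |
| 0.4, 0.3 | 0.12 | 55% | 31% |
| 0.4, 0.4 | 0.16 | 79% | 50% |

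The column for 150 covers the possibility that only half the target gives usable values.

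**2. The named tests themselves.** A simulation with 4,000 trials per scenario used a yes/no complication in 10, 25 or 50% of patients. At N = 300 and r1 = r2 = 0.1, 0.2, 0.3, 0.4, the t-test was significant in 5–6%, 11%, 34–35% and 79–80% of trials, and Kruskal-Wallis in 5%, 10–11%, 33% and 77–78%. A linear model with age (cubic) and sex gave 4.4–5.6% in all 30 scenarios.

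**3. Hiding an association.** Take a true same-age (partial) correlation of −0.15. The raw correlation is −0.15 × √((1 − r1²)(1 − r2²)) + r1 × r2.

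| r1 = r2 | raw correlation | unadjusted power, N = 300 |
|---|---|---|
| 0.1 | −0.1385 | 67% |
| 0.2 | −0.1040 | 44% |
| 0.3 | −0.0465 | 13% |
| 0.4 | +0.0340 | 9% |

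With age adjusted, atanh(0.15) × √296 = 2.60, which gives 74% power. At 0.4 the expected raw correlation has the wrong sign.

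**4. A second model.** This one assumed age uniform from 5 to 65, a complication in 25% of patients, an odds ratio of 1.2 to 2.0 per 10 years, N = 300 and 2,000 runs per setting. With no true link, the t-test was significant in 5–12% of runs at a metric–age correlation of −0.1, 11–62% at −0.3 and 22–97% at −0.5. With age in the model, the rate was 4.1–5.8% in every null setting. With a true difference of +0.4 SD, t-test power was 61–80%, 12–62% and 8–42% at those correlations, against 78–92% with age in the model. The pattern is the same under a different set of assumptions.

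**The case against.** The strongest reply is that Section 8 never spells out a comparison of a metric by complication status. Its one sentence on what is compared can be read with age and gender as the grouping side, and then age cannot confound the comparison. That stands, and it is why the point is conditional. On that reading, though, the group tests do not address the relation in Section 3.1.

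Second, a reader might infer that the plan has no way to adjust for age. The document does not support that: the hierarchical regression could include age, and because Section 8 bases each analysis on age and gender, it may already be meant to. Block order is often left to a statistical analysis plan. What remains is that the protocol itself fixes unadjusted tests whose results pass the same 0.05 screen, and an adjusted regression elsewhere does not correct them.

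Third, a reader might infer that the primary aim as a whole is confounded by age. That goes too far. Much of the aim concerns patterns over time, with each patient's own baseline as the comparison (Section 4.5.2), and within-patient change is largely untouched. Section 2.1 ties age to chronic complications and organ damage, not to acute crises or healthcare use.

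Fourth, every age correlation is assumed, and the large figures need strong ones. For a complication in 10% of patients, r2 = 0.3 means that affected patients are 0.3/√(0.1 × 0.9) = 1.0 SD older on average, and r2 = 0.4 means 1.33 SD. That is possible for organ damage but is not shown for outcomes in general.

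**Conclusion.** The point holds in a limited form. Where the Section 8 group tests, or a stepwise regression without age forced in, are used between patients to relate a wearable metric to a chronic complication or organ damage, age can create or hide an association if the metric also varies with age. Only the link between age and chronic complications is in the protocol, and only its direction. That any wearable metric changes with age is an assumption.

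At the target of 300, the effect is negligible when both age correlations are near 0.1 and material from about 0.3, where about a third of null comparisons would be flagged and power for a same-age correlation of −0.15 would fall from 74% to 13%. The 79% figure belongs to the strongest pair of correlations in the table and should not be read as the plan's error rate. The study is exploratory and flagged results go to further study, so the harm is a false or missed lead, not a wrong confirmatory claim. A change is worth making because it is cheap and concerns the kind of relation that the study sets out to find.

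**What to change.** Add to Section 8 that between-patient comparisons of wearable metrics with illness or healthcare utilisation are judged from the hierarchical regression already planned, or from ANCOVA, with a flexible age term and sex forced into the first block. Use logistic regression for yes/no outcomes; regressing the illness on the metric, age and sex also serves where the metric is not normally distributed. State that unadjusted t-test, ANOVA or Kruskal-Wallis results for these comparisons are descriptive only. Comparisons with age as the grouping factor and analyses of within-patient change stay as they are.

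Age and gender are already analysis variables, so no new data are needed, only a short addition to the text and minor programming. The price is a few degrees of freedom for the age term, and adjusted differences that are slightly less simple to report than raw group means.

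### Section 8 sends data with unequal variances to Kruskal-Wallis, which does not hold 5% as a test of equal location when group sizes are also unequal

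*Protocol*

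**What the plan says.** Section 8 (Statistical Analyses) checks the data "for normal distribution using Shapiro-Wilks testing, and for homogeneity of variance using Levene's testing". It then sets two routes. The first is "For data that do not violate these assumptions, either independent t-tests (for experiments with two experimental groups) or one-way ANOVA" for three or more groups, with Bonferroni post-hoc testing. The second is "Those that do violate these assumptions will undergo non-parametric Kruskal-Wallis testing".

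The assumptions in question include Levene's, so unequal variance is enough to send a variable down the second route even if it is normal. No Welch-type test is offered, and section 8 does not say which hypothesis Kruskal-Wallis is meant to test.

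The groups are observed, not allocated: "Each analysis will be based upon demographic variables, such as age and gender, correlated against genetic and clinical variables". The threshold is nominal: "Those with p-values below 0.05 will be considered as statistically significant and undergo further study". Section 4.1 sets the size: "our starting goal is to recruit 2% of the total UK SCD patient population, at 300 patients".

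**The concern.** Kruskal-Wallis takes its reference distribution from the case where all groups share one distribution. It can be read as a comparison of location only if the groups have similar shape and spread. A significant Levene test says that the spread is not shared, so the rule picks Kruskal-Wallis in the situation where that reading is weakest.

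The error can go either way. If the smaller group is the more variable one, the test rejects too often. If the larger group is, it rejects too rarely. Groups formed by genotype, age or comorbidity may well be uneven, because the design does not control their sizes. Some comparisons would then raise false leads and others would lose real signals, at the same nominal 0.05. The hypothesis also shifts with the pre-test: variables that pass are compared on means, and variables that fail are compared on whole distributions.

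**Working it through.** **The plan's own figure.** Section 4.1 states the population: "There is an estimated 12,500-15,000 people living with SCD in the UK". 0.02 × 15,000 = 300, which reproduces the target (the lower end gives 0.02 × 12,500 = 250). N = 300 is used below.

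**Inputs.** From section 8: nominal 5%, and the Shapiro-Wilk/Levene rule. Assumed, because the protocol gives none: group splits, SD ratios, normal data, equal means and medians.

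**Large-sample formula, two groups.** Kruskal-Wallis compares the share of between-group pairs in which one value exceeds the other with 0.5.
- Variance the test assumes: V0 = (1/12)(1/n1 + 1/n2).
- Actual variance for normal groups with equal centres: V = v1/n1 + v2/n2, where vi = arcsin[si²/(s1² + s2²)]/(2π). With equal SDs, vi = arcsin(0.5)/(2π) = 1/12, so V = V0.
- Rejection rate = 2[1 − Φ(1.96/√(V/V0))].

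*Example, 240/60, smaller group twice as variable.* v1 = arcsin(0.2)/(2π) = 0.03205 and v2 = arcsin(0.8)/(2π) = 0.14758. V = 0.03205/240 + 0.14758/60 = 0.002593. V0 = (1/12)(1/240 + 1/60) = 0.001736. V/V0 = 1.494, and 1.96/√1.494 = 1.604, which gives 10.9%.

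*Example, 240/60, larger group twice as variable.* V = 0.14758/240 + 0.03205/60 = 0.001149. V/V0 = 0.662, and 1.96/√0.662 = 2.41, which gives 1.6%.

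**Simulation of the whole rule** (t-test unless Shapiro-Wilk or Levene gives p<0.05, then Kruskal-Wallis). At 4,000 replicates the simulation error near 5% is √(0.05 × 0.95/4000) = 0.3 points. A range covers separate runs.

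| Split | More variable group | SD ratio | V/V0 | Formula | Simulated rule |
|---|---|---|---|---|---|
| 150/150 | either | 1.5 | 1.029 | 5.3% | 5.0% |
| 150/150 | either | 2 | 1.078 | 5.9% | 5.5-5.8% |
| 150/150 | either | 3 | 1.165 | 6.9% | 6.7-7.5% |
| 180/120 | smaller | 2 | 1.216 | 7.6% | 7.9% |
| 240/60 | smaller | 1.5 | 1.288 | 8.4% | 8.6-9.0% |
| 240/60 | smaller | 2 | 1.494 | 10.9% | 10.8-11.6% |
| 240/60 | smaller | 3 | 1.749 | 13.8% | 13.1-14.3% |
| 240/60 | larger | 2 | 0.662 | 1.6% | 1.7-1.9% |
| 240/60 | larger | 3 | 0.581 | 1.0% | 0.7-1.0% |

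Welch's test gave 4.4-5.2% in the 240/60 scenarios with ratios of 2 and 3, and 5.0% at 150/150 with the same ratios.

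**Why the rule behaves like Kruskal-Wallis here.** Levene rejects in 96% of samples at 240/60 with ratio 1.5, and in essentially all at ratios of 2 or more. At ratio 1.25 it rejects in only 55-72%, so the two routes mix.

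**Three groups.** With 200/70/30 and SDs 1:2:3, Kruskal-Wallis gives 14.7% and Welch ANOVA 5.2%. With SDs reversed to 3:2:1, Kruskal-Wallis gives 1.3% and Welch 4.8%. With 100/100/100 and SDs 1:2:3, they give 5.9% and 4.2%.

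**The case against.** Several points on the other side stand.

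- **The scenarios are assumptions.** Gender and age bands need not split 80/20. Near-even groups with moderate SD ratios show almost no distortion.
- **Kruskal-Wallis improves on the classical test where it matters most.** At 240/60 with the smaller group 2 or 3 times as variable, the ordinary t-test rejects 17.5% and 24.7% of the time, so the fallback cuts the error without removing it.
- **It is a valid test of identical distributions**, and section 8 never says it compares means or medians. It is also acceptable when only normality fails: with the same exponential distribution in both groups at 240/60, it rejects 5.0%.
- **Welch protects means only.** For exponential data with equal medians and SD ratio 2, Welch rejects 15.5% (240/60) and 38.5% (150/150), against 16.4% and 14.6% for Kruskal-Wallis. The target parameter has to be stated.

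A reader might infer that Kruskal-Wallis is simply the wrong test here, or that most variables, admission counts included, will be misjudged. The protocol supports neither. It gives no distributions, group sizes or spreads from which to say how many variables fail, or fail for spread and not shape. Nor is Kruskal-Wallis the whole analysis: section 8 also plans descriptive analysis, Q-Q plots and regression. Replacing it with specific count models goes beyond what this sentence shows to be wrong.

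What the objection does not remove is the stated Levene-to-Kruskal-Wallis route, which has no alternative for comparing means.

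**Conclusion.** The point holds in a conditional form. Section 8 fixes a fallback for unequal variance that does not keep the nominal rate for equal location unless the groups are near even in size. Under the assumed scenarios the distortion runs from negligible in balanced groups to roughly double or nearly triple the nominal rate at 240/60 with a more variable small group, and to well below nominal in the reverse case.

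This is a fault in a rule the protocol states, not a detail left to a later plan. Importance is moderate to low: section 8 calls the study exploratory, and a significant result leads only to further study.

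**What to change.** In section 8, replace the two-route rule with wording to this effect:

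- Continuous patient-level summaries are compared on means with Welch's t-test (two groups) or Welch ANOVA with Games-Howell post hoc (three or more), by default or at least whenever variances differ. The mean difference is reported with a 95% CI.
- Kruskal-Wallis is kept for ordinal or clearly skewed variables, and is described as a test of whether distributions differ, not of equal means or medians.

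The change is one of wording. The power cost when variances are equal is negligible: at 240/60 with a true difference of 0.4 SD, simulated power is 78.4% for the ordinary t-test and 78.0% for Welch.
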